7.3 Serious Adverse Events

7.3.1 Definitions of Serious Adverse Events

The definitions of serious adverse events (SAEs) are given below. The principal investigator is responsible for ensuring that all staff involved in the trial is familiar with the content of this section.

An SAE or reaction is defined as any untoward medical occurrence that: results in death, is immediately life-threatening, requires at least a 24-hour in-patient hospitalization or prolongation of existing hospitalization, results in persistent or significant disability/incapacity, or is a congenital anomaly/birth defect.

The definition of SAE also includes any important medical event. Medical and scientific judgment should be exercised in deciding whether expedited reporting is appropriate in other situations, such as important medical events that may not be immediately life-threatening or result in death or hospitalization, but may jeopardize the patient or may require intervention to prevent one of the other outcomes listed in the previous definition. These should also usually be considered serious. Examples of such events are intensive treatment in an emergency room or at home for allergic bronchospasm; blood dyscrasias or convulsions that do not result in hospitalization; or development of drug dependency or drug abuse. ***Progression of malignancy (including fatal outcomes), if documented by use of appropriate method (for example, as per Lugano classification 2014), should not be reported as a serious adverse event.***

Treatment within or admission to the following facilities is not considered to meet the criteria of “in-patient hospitalization” (although if any other SAE criteria are met, the event must still be treated as an SAE and immediately reported):

- Emergency Department or Emergency Room
- Outpatient or same-day surgery units
- Observation or short-stay in unit or short stay to facilitate PK blood draws
- Rehabilitation facility
- Hospice or skilled nursing facility
- Nursing homes, Custodial care or Respite care facility

Hospitalization during the trial for a pre-planned surgical or medical procedure (one which is planned prior to entry in the trial or planned in advance and not related to the study procedure/drug), does not require reporting as a serious adverse event to the Sponsor.

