7.4.4 Deaths

Deaths that occur during the protocol-specified AE reporting period that are attributed by the investigator solely to progression of disease will be recorded on the "Trial Discontinuation" eCRF and should not be reported as a SAE. All other on- trial deaths, regardless of attribution, will be recorded on an SAE Report and expeditiously reported to the Sponsor.

When recording a serious adverse event with an outcome of death, the event or condition that caused or contributed to the fatal outcome should be recorded as the single medical concept on the SAE report and Adverse Event page of the eCRF. If the cause of death is unknown and cannot be ascertained at the time of reporting, record "Death NOS" on the CRF Adverse Event page.

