7.4.9 Lack of Efficacy

When there is deterioration in the condition for which the study treatment is being used, there may be uncertainty as to whether this is lack of efficacy or an AE. In such cases, unless the sponsor or reporting physician considers the study treatment contributed to the deterioration of the condition, the deterioration should be considered lack of efficacy and not an AE.

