9.4.2 Safety Analyses

The safety endpoints will include:

- Incidence of DLTs
- Incidence of AEs and related AEs
- Incidence of grade 3 and grade 4 AEs
- Incidence of SAEs and death
- Laboratory values
- ECG/vital signs

The safety endpoints will be listed and/or summarized by dose cohort. No inferential statistical analyses will be performed.

The analyses of safety will be based on the frequency of adverse events and their severity for patients in each portion who received at least one dose of study treatment. Worst toxicity grades per patient will be tabulated for select adverse events and laboratory measurements by using NCI CTCAE criteria v5.0.

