## 10.6.2 Adverse Events

Analysis set: Safety

Note:

- If needed, adverse event data may be presented for all patients.
- The dose reduction information will be compiled using the treatment exposure page and AE page of eCRF through common AE number.

The frequency of adverse events (AEs) will be computed by counting each patient only once per MedDRA [Version 24.0] preferred term and according to the maximum NCI CTCAE v.5.0 grade attained by the patient over the specified period. The percentage of patients with an event will be calculated using the number of patients in the safety analysis set as the denominator.

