### **Standard Summaries of Adverse Events**

Treatment Emergent Adverse Events (TEAEs) are those that start on or after the date of first dose of study medication.

An overall summary of TEAEs (number and percentage of patients along with the number of events) will be presented with the following:

- Any TEAE
- Treatment Related TEAEs
- Serious TEAEs
- Treatment Related Serious TEAEs
- Grade 3 or 4 TEAEs
- Treatment Related Grade 3 or 4 TEAEs
- DLTs (Note: Applicable for dose escalation phase only)
- TEAEs leading to drug interruptions
- Related TEAEs leading to drug interruptions
- Serious TEAEs leading to drug interruptions
- Treatment Related Serious TEAEs leading to drug interruptions
- TEAEs leading to dose reduction
- Related TEAEs leading to dose reduction
- Serious TEAEs leading to dose reduction
- Treatment Related Serious TEAEs leading to dose reductions

- TEAEs leading to drug withdrawn permanently
- Treatment Related TEAEs leading to drug withdrawn permanently
- Serious TEAEs leading to drug withdrawn permanently
- Treatment Related Serious TEAEs leading to drug withdrawn permanently
- Fatal TEAEs
- Treatment Related Fatal TEAEs
- Protocol-Defined Adverse Events of Special Interest:
  - Pregnancy, abortion, birth defects/congenital anomalies
  - Overdose

Summaries showing the number of patients (n, %) along with number of events by SOC and PT will be provided for the following:

- DLTs (Note: Applicable for dose escalation phase only)
- TEAEs
- Related TEAEs
- Non-TEAEs
- Grade 3, 4 and 5 TEAEs
- Related Grade 3, 4 and 5 TEAEs
- Treatment-Emergent SAEs
- Related Treatment –Emergent SAEs
- TEAE with maximum CTCAE grade
- Treatment-Related TEAEs with maximum CTCAE grade per suspected drug(s) [Tenalisisib, Romidepsin or Combination]
- Deaths
- TEAEs leading to drug interruptions
- TEAEs leading to dose reduction
- TEAE leading to drug withdrawn permanently

The adverse events data will also be listed for individual patients.

- Any non-TEAE
- TEAEs
- Related TEAEs
- SAEs
- Treatment Emergent Grade 3, 4 and 5 AEs
- Treatment Related Grade 3, 4 and 5 AEs
- Treatment Related SAEs
- TEAEs leading to drug interruptions
- TEAEs leading to dose reduction
- TEAE leading to drug withdrawn permanently

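### Every death count in the SAP rests on adverse-event records, so deaths put down solely to progression go uncounted although Protocol 9.4.2 makes incidence of death a safety endpoint

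*SAP*

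**What the plan says.** **The endpoint.** Protocol 9.4.2 lists "Incidence of SAEs and death" among the safety endpoints. Death is named next to SAEs and is not limited to fatal adverse events. The endpoints are to be listed, summarised or both, by dose cohort, without inferential tests.

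**The planned outputs.** In SAP 10.6.2, under Standard Summaries of Adverse Events, Deaths is one item on a list that opens: "Summaries showing the number of patients (n, %) along with number of events by SOC and PT will be provided for the following". The section's counting rule is "counting each patient only once per MedDRA [Version 24.0] preferred term". The overall TEAE summary also has a line for fatal TEAEs and one for "Treatment Related Fatal TEAEs".

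**Where deaths are recorded.**
- Protocol 7.4.4: "Deaths that occur during the protocol-specified AE reporting period that are attributed by the investigator solely to progression of disease will be recorded". The form named there is the Trial Discontinuation eCRF, and these deaths are not SAEs. Every other on-trial death goes on an SAE report.
- Protocol 7.3.1: "Progression of malignancy (including fatal outcomes), if documented by use of appropriate method", is likewise kept out of SAE reporting.
- Protocol 7.4.8 treats new lesions and symptoms of metastasis as progression, not as AEs or SAEs. Under Protocol 7.4.9, unless treatment is thought to have contributed, "the deterioration should be considered lack of efficacy and not an AE".
- Protocol 7.3.2: deaths more than 30 days after the last treatment and not attributed to it go on an eCRF page but not into SAE reporting.

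**The concern.** The endpoint is death; the outputs count fatal adverse events. In relapsed or refractory T-cell lymphoma some on-study deaths can be expected to be ascribed to progression, and those are the deaths the recording rules send to a different page. A study report produced exactly to this SAP would carry a table headed Deaths that omits them.

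The second issue is dependence on attribution. The study is open-label, without a control arm, and the investigator decides whether a death is solely due to progression. The call can be hard: Protocol 3.4.5.2 reports fatal infections, including sepsis, during romidepsin treatment and within 30 days after it, and Protocol 1.1.2 reports treatment-related sepsis and bacteremia with tenalisib. An all-cause count does not depend on that judgement, and a listing lets a reader look at each case.

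**Working it through.** The documents state no figure on this point, so there is none to reproduce. The main check traces where each kind of death is recorded and which planned output could show it.

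| Type of death | Recorded as | SAP death output that counts it |
|---|---|---|
| On-trial, not solely progression | SAE report (Protocol 7.4.4) | Deaths by SOC/PT; fatal TEAEs |
| On-trial, solely progression | Trial Discontinuation eCRF, not an SAE (7.4.4, 7.3.1); progression generally not an AE (7.4.8, 7.4.9) | None specified |
| More than 30 days after last treatment, not attributed to it | An eCRF page, not an SAE (7.3.2) | None specified |

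The second row is the gap. With no AE record there is no preferred term to count.

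**Other outputs that might fill it**
1. Patient disposition (SAP 10.1) gives reasons for dropout. It is not specified to show death, its cause or its timing. A patient who stops for progression and dies during the 30-day follow-up could appear there as progression only.
2. SAP section 14 lists study completion and reasons for discontinuation, with the same limits. Neither that section nor the AE listings in SAP 10.6.2 include a death listing.
3. Efficacy (SAP 4.2, 10.5) covers response rate and duration of response. Neither progression-free nor overall survival is an endpoint, and SAP 10.5.2 censors patients who die without progression.
4. Combined eCRF pages: SAP 10.6.2 says explicitly that dose-reduction data come from two pages. It says nothing similar for deaths.

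**Illustration of size.** The numbers of deaths are assumptions. Planned maximum N = 18 (escalation, three dose levels) + 24 (expansion) = 42. Let a be deaths recorded as fatal AEs and k be progression deaths. The SAP reports a/42; all-cause incidence is (a + k)/42. Intervals are exact (Clopper-Pearson): for x of n, the lower limit is the 2.5% point of Beta(x, n − x + 1) and the upper limit the 97.5% point of Beta(x + 1, n − x). With a = 1:

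| k (assumed) | SAP death table | All-cause |
|---|---|---|
| 0 | 1/42 = 2.4% (0.1 to 12.6) | 1/42 = 2.4% (0.1 to 12.6) |
| 2 | 1/42 = 2.4% (0.1 to 12.6) | 3/42 = 7.1% (1.5 to 19.5) |
| 4 | 1/42 = 2.4% (0.1 to 12.6) | 5/42 = 11.9% (4.0 to 25.6) |
| 8 | 1/42 = 2.4% (0.1 to 12.6) | 9/42 = 21.4% (10.3 to 36.8) |

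The middle column does not move with k.

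**Attribution in a small group.** If the only fatal toxicity in a 12-patient expansion group were ascribed solely to progression, fatal TEAEs would read 0/12 (0 to 26.5%) instead of 1/12 = 8.3% (0.2 to 38.5%).

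**The case against.** **The wording is ambiguous and does not expressly exclude these deaths.** The SAP lists Deaths separately from fatal TEAEs and does not say that only AE pages feed it. This stands as far as it goes: a programmer might read in the discontinuation page. But the table sits among the AE summaries and is organised by SOC and PT, and no rule is given for coding a progression death.

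**Protocol 9.4.2 does not require a table.** True, a listing would satisfy it. No death listing is planned either.

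**The AE exclusion is inferred.** Protocol 7.4.4 and 7.3.1 exclude these deaths from SAE reporting. The step to no AE record comes from 7.4.8 and 7.4.9, and the latter makes an exception where treatment is thought to have contributed. Hence the claim is that such deaths normally, not always, lack a SOC and PT.

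**A reader might infer that a misattributed toxic death vanishes from the safety data.** The documents do not support that. Protocol 7.1.2 requires all AEs to be recorded whatever their relationship to treatment, 7.3.2 requires SAEs regardless of causality up to 30 days, and 7.2 presumes toxicities related unless there is a clear alternative. A sepsis before death would still be recorded as an event. What would be missing from the death outputs is its fatal outcome, and only if the death is ascribed solely to progression.

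**The eCRF is not among the documents.** Whether date and cause of death are captured separately from the reason for discontinuation cannot be confirmed. This stands and qualifies the cost.

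**Conclusion.** The concern holds as a mismatch between the safety endpoint in Protocol 9.4.2 and the death outputs in SAP 10.6.2. Followed as written, the SAP reports fatal adverse events, not incidence of death. It rests on the recording rules in Protocol 7.3.1, 7.4.4, 7.4.8 and 7.4.9, and on reading the SOC/PT table as drawn from coded AE records.

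The size is unknown because no death rate is given. The shortfall equals the number of progression deaths without an AE record; the 42-patient table shows its effect for assumed counts only and predicts nothing.

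Two further inferences are tempting and should not be drawn:
- *That the primary endpoint is compromised.* That endpoint (Protocol 3.1.1, SAP 4.1) is adverse events, including fatal ones. True progression deaths properly fall outside it.
- *That the SAP weakens the accrual suspension after a drug-attributed death.* Protocol 3.6.2 turns on attribution while the trial is running. A table in the final analysis neither triggers nor blocks it.

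No dose decision, DLT rule or efficacy result is shown to change. The point still merits a SAP change, because it alters a reported safety result.

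**What to change.** In SAP 10.6.2:

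1. Relabel the SOC/PT Deaths table as fatal TEAEs.
2. Add an all-cause death table for the safety set, and name its sources: the AE, SAE and Trial Discontinuation pages and any other eCRF page that captures a death. Show deaths within 30 days of the last dose, and separately any later deaths captured, with a note that follow-up beyond 30 days is incomplete because Protocol 6.13 plans only the 30-day contact. Split by investigator-assigned cause, dose level and PTCL/CTCL. The total does not depend on attribution; the split by cause does, and should be labelled so.
3. Add a death listing with cause, days since last dose and AEs ongoing at death.

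The cost is SAP wording, one table and one listing. Protocol 7.4.4 and 7.3.2 already require these deaths to be recorded, so no new data collection should be needed, provided the eCRF holds the date and cause of death; that should be checked first.

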### 10.6.3 Clinical Laboratory Tests

Analysis Set: Safety

Laboratory data will be presented per cycle for each phase.

Baseline will be defined in each phase of the study. The baseline measurement will be the last pre-treatment measurement taken on or before Cycle1 Day1 in respective phase. For Dose Escalation phase, the baseline will be the last pre-treatment measurement taken on or before the Cycle 1 Day 1 dose for Romidepsin, and for Dose Expansion phase, the baseline will be the last pre-treatment measurement taken on or before Cycle 1 Day 1 dose of Romidepsin or Tenalisib whichever is earlier.

Absolute values of laboratory parameters will be presented at each visit using descriptive statistics (n, mean, median, standard deviation, minimum and maximum values).

The laboratory data will also be listed.

A separate listing of patients with abnormal laboratory test values will also be presented.

Hematology	Chemistry Panel I	Chemistry Panel II	Urinalysis	Other
Hematocrit	Total bilirubin	Blood glucose	Blood	PT
Hemoglobin	Alkaline phosphatase (ALP)	Urea or blood urea nitrogen	Glucose	INR
CBC with differentials	Alanine aminotransferase (ALT)	Albumin	Protein	
Platelet count	Aspartate aminotransferase (AST)	Total protein	Specific gravity	
WBC (Total and differentials)	Lactate dehydrogenase (LDH)	Total Cholesterol	Microscopic exam	
Red blood cell count	Gamma-glutamyl transferase	Triglyceride (TG)		
Absolute neutrophil count	Sodium	LDL		
Absolute lymphocyte count	Potassium	HDL		
	Calcium	TSH		
	Phosphorous	T3 (Total or Free)		
	Bicarbonate or Carbon Dioxide (CO2)	T4 (free)		
	Chloride	Creatinine		
	Magnesium			

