9.1 General Considerations

Unless otherwise stated, all statistical analyses will be performed using a two-sided hypothesis test at the overall 5% level of significance. The primary efficacy endpoint for the Phase II trial will be evaluated at a one-sided 5% level. No adjustment for Type I error rate will be required because the study has only one primary endpoint with one comparison. P-values will be rounded to three decimal places. If a p-value is less than 0.001 it will be reported as “<0.001”.

Continuous data will be described using the following descriptive statistics: n, mean, median, minimum and maximum. Data will be displayed in all listings sorted by phase, group and patient number. When count data are presented, the percentage will be suppressed when the count is zero in order to draw attention to the non-zero counts. A row denoted “Missing” will be included in count tabulations where necessary to account for dropouts and missing values. Unless otherwise specified, the denominator for percentages will be the number of patients with a non-missing assessment in a given treatment group within the analysis population of interest.

All statistical analyses will be performed using SAS 9.1 or higher.

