### 10.6.5 Vital Signs

#### Analysis Set: Safety

Vital signs will include pulse rate, respiratory rate, blood pressure, and temperature (oral/axillary). Weight will also be included here.

Baseline will be defined in each phase of the study. The baseline measurement will be the last pre-treatment measurement taken on or before Cycle1 Day1 in respective phase. For Dose Escalation phase, the baseline will be the last pre-treatment measurement taken on or before the Cycle 1 Day 1 dose for Romidepsin, and for Dose Expansion phase, the baseline will be the last pre-treatment measurement taken on or before Cycle 1 Day 1 dose of Romidepsin or Tenalisib whichever is earlier.

Absolute values of Vital Signs data will be summarized descriptively (n, mean, median, standard deviation, minimum and maximum) per cycle for every scheduled timepoint. A listing will also be provided.

A separate listing of patients with abnormal vital signs findings will also be presented.

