### 10.6.6 Electrocardiogram

#### Analysis Set: Safety

- Baseline will be defined in each phase of the study. The baseline measurement will be the last pre-treatment measurement taken on or before Cycle1 Day1 in respective phase. For Dose Escalation phase, the baseline will be the last pre-treatment measurement taken on or before the Cycle 1 Day 1 dose for Romidepsin, and for Dose Expansion phase, the baseline will be the last pre-treatment measurement taken on or before Cycle 1 Day 1 dose of Romidepsin or Tenalisib whichever is earlier.
- Absolute values of ECG parameters [PR Interval, HR (heart rate), QT interval, QTcF (QT interval with Fridericia's correction), QRS Duration] as collected on CRF will be presented through n, mean, median, standard deviation, minimum, and maximum per cycle for every scheduled timepoint.
- A summary of abnormal ECG results will also be provided per cycle in each phase including baseline visit using frequencies and percentages.
- A listing of this data will also be provided.
- A separate listing for the abnormal ECG values will also be presented.

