### 10.6.7 ECOG

#### Analysis Set: Safety

Baseline will be defined in each phase of the study. The baseline measurement will be the last pre-treatment measurement taken on or before Cycle1 Day1 in respective phase. For Dose Escalation phase, the baseline will be the last pre-treatment measurement taken on or before the Cycle 1 Day 1 dose for Romidepsin, and for Dose Expansion phase, the baseline will be the last pre-treatment measurement taken on or before Cycle 1 Day 1 dose of Romidepsin or Tenalisib whichever is earlier.

ECOG performance status (0=Normal activity, 1=Symptoms, but ambulatory, 2=In bed < 50% of the time, 3 and above=In bed > 50% of the time or 100% bedridden or are Dead), as reported in the eCRF, will be summarized per cycle in each phase with number and percentage for each status category. This data will also be listed.

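### SAP 10.6.3 and 10.6.5 to 10.6.7 define a baseline but plan no change-from-baseline or shift summary, so visit tables can mix drug effect with attrition

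*SAP*

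**What the plan says.** SAP 10.6.3 (laboratory tests), 10.6.5 (vital signs), 10.6.6 (ECG) and 10.6.7 (ECOG) use the same baseline rule: "The baseline measurement will be the last pre-treatment measurement taken on or before Cycle1 Day1 in respective phase". Each adds which drug's first dose counts in each phase.

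The planned summaries are:

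- **Laboratory:** "Absolute values of laboratory parameters will be presented at each visit using descriptive statistics". For abnormal results: "A separate listing of patients with abnormal laboratory test values will also be presented".
- **Vital signs:** "Absolute values of Vital Signs data will be summarized descriptively", by cycle and scheduled time point, with listings.
- **ECG:** "Absolute values of ECG parameters", QTcF among them, by cycle and time point. In addition: "A summary of abnormal ECG results will also be provided per cycle in each phase including baseline visit using frequencies and percentages".
- **ECOG:** status "will be summarized per cycle in each phase with number and percentage for each status category". Grades 3, 4 and death form one category.

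The default percentage rule in Protocol 9.1, repeated in SAP 10, is that "the denominator for percentages will be the number of patients with a non-missing assessment". The adverse event tables in SAP 10.6.2 instead divide by the whole safety set.

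Protocol 9.4.2 also plans a tabulation of each patient's worst CTCAE grade for laboratory measurements. SAP 10.6.3 does not carry it over.

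**The concern.** A baseline is normally defined so that each patient can be compared with himself or herself. Here that comparison is left to the reader of the listings. The reader of the tables can only compare a visit mean, taken over those still assessed, with a baseline mean taken over everyone.

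The two sets of patients can differ. Entry criteria allow a wide spread (Protocol 4.1: platelets from 75,000/µL; AST/ALT up to 3 times ULN, or 5 times with liver involvement; ECOG 0 to 2). Patients stop for progression, toxicity or withdrawal before C8D1 (Protocol 4.3 and 8.2). Columns are small: 3 to 6 per escalation cohort and 12 per expansion group. If those who leave tend to have high or low values, a visit mean can move although nobody changed, or stay still although everyone changed.

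The protocol itself reasons from the individual's baseline. Table 8 refers to QTcF relative to baseline, and several restart criteria in section 7.7 refer to a return to baseline. The SAP does not summarise that quantity.

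**Working it through.** The plan has no figure to reproduce: SAP 9.1 states that no hypothesis is tested, and no dropout rate or standard deviation is given. The check has two parts.

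**1. Is baseline used?** The four sections were read for any change from baseline, shift table, or worst post-baseline grade. None is specified. The one stated use is the baseline visit in the abnormal-ECG table, which gives separate counts at each visit and does not show which patients moved.

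**2. How far can a visit mean mislead?** For any numeric parameter,

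visit mean − baseline mean of all = (mean paired change in those remaining) + (baseline mean of those remaining − baseline mean of all).

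The first term is the quantity of interest. The second is attrition alone.

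*Platelets, assumed values (x10^9/L).* Twelve patients, 4 at 80 and 8 at 200; the 4 leave and the other 8 each fall by 30.
- Baseline mean of all: (4×80 + 8×200)/12 = 160.
- Visit mean: 200 − 30 = 170.
- Apparent change: 170 − 160 = +10 = (−30) + (200 − 160).
- Each remaining patient fell by 30/200 = 15%.

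*QTcF, assumed values (msec).* Twelve baselines: 400, 405, 410, 415, 420, 425, 430, 435, 440, 445, 448, 450; mean 426.9. The four highest leave; the other eight have baseline mean 417.5.
- True rise of 10 in each: visit mean 427.5, apparent change +0.6 against a paired change of +10.
- No true rise: apparent change 417.5 − 426.9 = −9.4 against a paired change of 0.

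*General size.* Simulation of 12 patients with no drug effect, k leaving, and correlation ρ between the value and the tendency to leave (both assumed). Expected shift in the visit mean, in between-patient SDs, when patients with higher values tend to leave:

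| k leaving | ρ = 0 | ρ = 0.3 | ρ = 0.5 | ρ = 1 |
|---|---|---|---|---|
| 2 | 0 | −0.08 | −0.14 | −0.27 |
| 4 | 0 | −0.15 | −0.25 | −0.51 |
| 6 | 0 | −0.22 | −0.37 | −0.75 |

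The paired change is 0 in every cell.

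*ECOG.* With 12 assessed and, say, 4 at grade 2, the share at 0 to 1 is 8/12 = 67%. If those 4 are not assessed at C3D1 and nobody else changes, it becomes 8/8 = 100%.

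**The case against.** A reader might infer that the baseline is never used, that nothing but absolute values is summarised, or that attrition will necessarily appear as a drug effect. The documents do not support any of these. The abnormal-ECG table includes the baseline visit, and ECOG is tabulated by category. Distortion needs leaving to be related to the value: in the ρ = 0 column it is zero, and with 2 of 12 leaving at ρ = 0.3 it is 0.08 SD. The platelet and QTcF examples remove exactly the extreme patients, so they show what is possible and not what is likely.

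Nor do these tables carry the primary endpoint. That is adverse events by CTCAE (Protocol 3.1.1, SAP 4.1), and DLTs are judged patient by patient. Grade 3 or 4 laboratory values and clinically significant Grade 1 or 2 values are to be recorded as adverse events (Protocol 7.4.3). They are then tabulated at maximum grade over the safety set, a denominator that does not shrink. The numeric tables show n, and listings allow individual before-and-after reading. ECOG is scheduled at EOT, so many early leavers should have a later value.

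Most of this stands and limits the point; it does not remove it. Protocol 7.4.3 lets isolated laboratory abnormalities without clinical significance go unrecorded as adverse events, so moderate drift can miss those tables. The abnormal-ECG counts cannot separate patients who changed from patients who left. Listings hold the data but summarise nothing. The protocol's own worst-grade laboratory table, which would help most, is missing from SAP 10.6.3.

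**Conclusion.** The point holds in limited form. The four sections define a baseline and specify no within-patient summary from it. Visit means for laboratory tests, vital signs and ECG, and ECOG percentages on non-missing patients, can therefore confound drug effect with attrition. The affected outputs are supportive safety summaries, chiefly moderate drift in laboratory values, vital signs and QTcF, and ECOG. The primary adverse event analysis is not undermined, and a reader should not conclude that it is.

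The size cannot be fixed from the documents. For a group of 12 with 2 to 6 leaving, the distortion runs from zero, if leaving is unrelated to the value, to about 0.75 SD, if leaving is wholly determined by it and half leave. Dropout and correlation are assumptions. The change is worth making because a better summary costs almost nothing once baseline is defined and collected.

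**What to change.** Revise the SAP as follows.

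- **10.6.3, 10.6.5, 10.6.6:** keep the absolute values. For each numeric parameter add within-patient change from the defined baseline at each scheduled time point, showing the number with both values and the baseline mean of those same patients. Add change from baseline to the last on-treatment value, because paired change at a visit still describes only those who remain.
- **10.6.3:** restore the worst post-baseline CTCAE grade per patient that Protocol 9.4.2 plans, cross-tabulated against baseline grade.
- **10.6.7:** keep the per-cycle counts and add a shift table of baseline ECOG against C3D1 and against EOT/C8D1, the post-baseline visits at which ECOG is scheduled. Show death separately from ECOG 3 and 4.

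The cost is a derived change variable, some extra table rows and the SAP wording. No new data are needed.
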